### **13.6 Protocol amendments**

Any change or addition to the protocol can only be made in a written protocol amendment that must be approved by Novartis, health authorities where required, and the IRB/IEC prior to implementation.

Only amendments that are required for subject safety may be implemented immediately provided the health authorities are subsequently notified by protocol amendment and the reviewing IRB/IEC is notified.

Notwithstanding the need for approval of formal protocol amendments, the investigator is expected to take any immediate action required for the safety of any subject included in this study, even if this action represents a deviation from the protocol. In such cases, Novartis should be notified of this action and the IRB/IEC at the study site should be informed according to local regulations.

## 15 Appendices

### 15.1 Appendix 1: Clinically notable laboratory values and vital signs

#### Clinically notable laboratory values

The following criteria will be used to define expanded limits and notable abnormalities of key laboratory tests.

No specific action is pre-defined within this protocol to respond to specific abnormal laboratory values, as it will be decided by the investigator whether and which specific action needs to be taken to respond to any abnormal values, taking into account the overall status of the subject.

#### Liver Function and Related Variables

Alanine transaminase (ALT) (SGPT):  $> 3 \times$  Upper Limit of Normal (ULN)

Aspartate transaminase (AST) (SGOT):  $> 3 \times$  ULN

Total bilirubin:  $> 2 \times$  ULN

Alkaline phosphatase:  $> 2.5 \times$  ULN

#### Renal Function

Creatinine (serum):  $> 1.5 \times$  ULN

#### Hematology

Hemoglobin:  $\geq 2$  g/dl decrease from baseline

Platelet count:  $<$  Lower Limit of Normal (LLN)

White blood cell count:  $< 0.8 \times$  LLN

Neutrophils:  $< 0.9 \times$  LLN

[figure not shown]
Eosinophils:  $> 1.1 \times$  ULN

Lymphocytes:  $> 1.1 \times$  ULN

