marketing experience since its first approval for moderate to severe plaque-psoriasis in 2015. Approximately 4,000 patients with moderate to severe plaque-psoriasis were included in the studies of the registration program. This included 3,430 subjects treated with secukinumab in 10 phase II/III studies, 2,727 of whom were treated for at least 6 months and 2,029 of whom were treated for at least 48 weeks. Details of the risks and benefits are outlined in the current version of the Investigator's Brochure. The safety data from the completed and ongoing studies including AE and SAE data, laboratory parameters and immunogenicity data demonstrate a favorable safety profile. Observed risks include infections, in particular, upper respiratory tract infections, neutropenia and hypersensitivity reactions that can be seen with administration of foreign proteins. Most of the infections were non-serious, mild to moderate in severity, clinically easily manageable and did not lead to treatment discontinuation. Cases of neutropenia were uncommon, generally mild to moderate and transient and did not lead to treatment discontinuation, and only a few cases were temporally associated with non-serious infections. Subjects with pre-existing malignancies within the past 5 years are generally excluded from studies with secukinumab although there is no scientific basis to suggest that secukinumab would increase the risk for malignancies.

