### 8.4.1 Laboratory evaluations

A central laboratory will be used for analysis of all specimens listed below, unless noted otherwise. Details on the collections, shipment of samples and reporting of results by the central laboratory are provided to investigators in the laboratory manual. Refer to the Laboratory Manual for identification of laboratory reference range values and the schema for notification of site staff and Novartis for out of range values.

Subjects should avoid smoking within the hour preceding the blood draws. Appendix 1 ([Section 15.1](#)) shows the extended laboratory ranges that are considered clinically notable. No specific action is pre-defined within this protocol to respond to specific abnormal laboratory values, as it will be decided by the investigator whether and which specific action needs to be taken to respond to any abnormal values, taking into account the overall status of the subject.

The tests will be conducted as defined in the assessment schedule.

Test Category	Test Name
Hematology	Hematocrit, Hemoglobin, Platelets, Red blood cells, White blood cells, Differential (Basophils, Eosinophils, Lymphocytes, Monocytes, Neutrophils)

Chemistry	Albumin, Alkaline phosphatase, ALT, AST , Gamma-Glutamyl-Transferase (GGT), Lactate Dehydrogenase (LDH), Bicarbonate, Calcium, Magnesium, Phosphorus, Chloride, Sodium, Potassium, Creatinine, Total Bilirubin, Total Cholesterol, LDL, HDL, Total Protein, Triglycerides, Urea, Uric Acid, HbA1c, hs-CRP (will not be communicated to the site staff, incl. the investigator, or to Novartis during the study to maintain blinding)
Hepatitis Screening	Hepatitis screening will be conducted at the screening visit.
Pregnancy Test	Serum / Urine pregnancy test

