**Table 2-4 Rules for selecting values for analysis within a given visit window**

Timing of measurement	Type of data	Rule
Baseline	All data	See Section 2.1.1.2
Post-baseline efficacy	All data except for PRO (e.g., IGA)	The measurement closest to the target day will be used. In the event two measurements are taken equally apart (e.g., 1 day before target date and 1 day after), the results from the earlier visit will be used. If two measurements are taken on the same day, then select the first one using eCRF visit number. If two measurements have been taken on the same day and same visit then select the worst.
	PRO data	The measurement closest to the target day will be used. In the event two measurements are taken equally apart (e.g., 1 day before target date and 1 day after), the earlier one will be used. If two measurements have been taken on the same day, select the worst. If two measurement have the same value, select the first one using eCRF visit number.
Post-baseline safety	Summary information (e.g. laboratory values, vital signs, etc.)	The (non-missing) measurement closest to the target day will be used. In the event two measurements are taken equally apart (e.g. 1 day before target date and 1 day after) the first one will be used. If two measurements are taken on the same day then select the first one (using the time). If two measurements are taken on the same date/time then use the first visit number (assuming this is the planned visit). If two measurements are taken on the same date/time/eCRF visit number then use the average of two assessments.
Post-baseline safety	Notable abnormalities for laboratory values	The most extreme measurement in the window will be used. Note this means a subject can have a notably high and notably low measurement within an analysis period.

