## **2.7.3 Laboratory data**

The summary of laboratory evaluations will be presented for two groups of laboratory tests (hematology and serum chemistry). Descriptive summary statistics for the change from baseline to each study visit will be presented. These descriptive summaries will be presented by cohort, test group, laboratory test and treatment group. Change from baseline will only be summarized for subjects with both baseline and post baseline values. In addition, Summary of notable abnormalities of key laboratory tests will be provided by treatment group. Detail on notable abnormalities derivations will be specified in [Section 5.3](#).

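### The notable-laboratory table counts high lymphocytes but not low ones, so it gives no count by arm of subjects with lymphopenia

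*Protocol*

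**What the plan says.** The hematology list in Protocol 15.1 (Appendix 1) sets low-direction limits for two related counts: "White blood cell count: $< 0.8 \times$ LLN" and "Neutrophils: $< 0.9 \times$ LLN". Platelets are also flagged when low, and hemoglobin is flagged on a fall from baseline. Eosinophils and lymphocytes are flagged only when high; the lymphocyte line is "Lymphocytes: $> 1.1 \times$ ULN". SAP 5.3 repeats the same lymphocyte criterion, and its list runs without a gap.

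SAP 2.7.3 plans the table: "Summary of notable abnormalities of key laboratory tests will be provided by treatment group". It then points to SAP 5.3 for the definitions ("Detail on notable abnormalities derivations will be specified in" that section). SAP Table 2-4 takes the most extreme value in the window for this table and comments: "Note this means a subject can have a notably high and notably low measurement within an analysis period".

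Lymphocytes are already measured. Protocol 8.4.1 includes "Differential (Basophils, Eosinophils, Lymphocytes, Monocytes, Neutrophils" in the hematology panel. Protocol 15.1 attaches no predefined action to a notable value.

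**The concern.** Protocol 4.6 states: "Observed risks include infections, in particular, upper respiratory tract infections, neutropenia and hypersensitivity reactions". Infection comes first in that list, and Protocol 8.4.3 describes the drug as a biologic, immunomodulating agent. Under Protocol Table 6-2, patients may be randomized 4 weeks after stopping methotrexate, cyclophosphamide, azathioprine or mycophenolate. A reader of the safety tables would expect to see how many subjects in each arm had a low lymphocyte count.

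As written, a lymphocyte count slightly above 1.1 times the upper limit of normal (ULN) is counted as notable, while a count far below the lower limit of normal (LLN) is not. Neither document gives a reason for the one-directional limit. What is at stake is the completeness of one safety table.

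**Working it through.** The plan states no figure to reproduce. The check has two parts: the direction of each criterion, and whether the white-cell criterion catches low lymphocytes indirectly.

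**1. Direction of each listed criterion (Protocol 15.1 and SAP 5.3)**

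| Test | Low limit | High limit |
|---|---|---|
| ALT, AST | none | > 3 x ULN |
| Total bilirubin | none | > 2 x ULN |
| Alkaline phosphatase | none | > 2.5 x ULN |
| Creatinine | none | > 1.5 x ULN |
| Hemoglobin | fall of at least 2 g/dl (20 g/l) | none |
| Platelets | < LLN | none |
| White cells | < 0.8 x LLN | none |
| Neutrophils | < 0.9 x LLN | none |
| Eosinophils | none | > 1.1 x ULN |
| Lymphocytes | none | > 1.1 x ULN |

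No laboratory test has limits in both directions. For vital signs, SAP Table 2-7 does set limits on both sides.

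**2. Does the white-cell limit cover it?**

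The documents give no reference ranges, so these are assumptions (x10^9/L): white-cell LLN 3.5 to 4.5, neutrophil LLN 2.0, lymphocyte LLN 1.0 and ULN 4.0.

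- White-cell cut: 0.8 x 3.5 = 2.8, up to 0.8 x 4.5 = 3.6.
- Neutrophil cut: 0.9 x 2.0 = 1.8.
- Lymphocyte (high) cut: 1.1 x 4.0 = 4.4.

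Example subject: neutrophils 3.0, lymphocytes 0.3, other cells 0.4.

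- Total white cells: 3.0 + 0.3 + 0.4 = 3.7, above 3.6, so no flag anywhere in the assumed range.
- Neutrophils: 3.0 against 1.8, no flag.
- Lymphocytes: 0.3 / 1.0 = 30% of the assumed LLN, no flag because no limit exists.
- By contrast, a lymphocyte count of 4.5 exceeds 4.4 and is flagged.

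A grid of cases gives the same picture. Baseline lymphocytes were 1.5 or 2.0, falling to 0.2 or 0 with other cells unchanged, and white-cell LLN was 3.5, 4.0 or 4.5.

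| Baseline white cells | Cases | White-cell total after the fall | White-cell flag raised |
|---|---|---|---|
| 6, 7, 8 or 10 | 4 x 2 x 2 x 3 = 48 | 4.0 to 8.7 | 0 |
| 4.5 or 5.0 | 2 x 2 x 2 x 3 = 24 | 2.5 to 3.7 | 13 |

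The flag appears only when the total was near its lower limit to begin with, and then it is labelled as low white cells. These are chosen cases, not expected frequencies.

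**3. Why the change-from-baseline summary is not a substitute**

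On the same assumed limits, a subject falling from 2.0 to 1.0 shows a change of 1.0 - 2.0 = -1.0 and ends at the LLN. A subject falling from 1.0 to 0.3 shows 0.3 - 1.0 = -0.7 and ends far below it. The size of the change does not identify who is low. SAP Table 2-4 also uses the value closest to the target day for these summaries, and keeps the most extreme value for the notable table alone.

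**The case against.** The strongest case against is that low lymphocytes are visible by several other routes.

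- SAP 2.1 includes the minimum and quartiles in every continuous summary, so the largest fall in each group is shown by visit.
- Protocol 10.1.1 requires review of values outside normal ranges, not only those on the notable list. Values that are clinically significant, symptomatic or need therapy become adverse events and are tabulated.
- Protocol 8.4.1 provides for notifying site staff and the sponsor of out-of-range values.
- The low white-cell row catches some cases.
- Exclusion criterion 15 removes patients whose laboratory abnormalities, in the investigator's opinion, significantly immunocompromise them.

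All of this stands. A reader might infer from the criteria list that a severe lymphopenia would go unseen; these routes show otherwise. They do not supply a count of subjects below a stated limit by arm. The adverse-event table counts only cases an investigator judged significant.

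Two further inferences go too far. One is that the drug carries a lymphopenia risk: Protocol 4.6 names neutropenia as the only cytopenia, and that is flagged low. The other is that SAP Table 2-4 proves a lower limit was dropped by mistake. Its note speaks of a subject, not of one test, and high eosinophils with low neutrophils in one subject would satisfy it. It sits awkwardly with a list of one-directional limits but does not strictly contradict it.

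**Conclusion.** The point holds as a gap in one reporting table. The notable-abnormality table, as defined, has no low-lymphocyte row and cannot give the number of subjects with lymphopenia in each arm. That follows directly from the two criteria lists and needs no assumption.

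That the white-cell row often fails to catch such cases rests on assumed reference limits: no flag in the 48 cases starting at 6 or above, and a flag in 13 of the 24 starting at 4.5 or 5.0. How many trial subjects would be affected cannot be estimated from the documents. They also do not show whether the high-only limit was intended.

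This is a minor improvement. It changes no efficacy result, no sample-size figure and no patient management.

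**What to change.** In Protocol 15.1 and SAP 5.3, keep the upper lymphocyte limit and add a low-direction one. The sponsor should choose the multiple of LLN; 0.8 and 0.9 are already in use for white cells and neutrophils, and the documents give no basis for preferring either for lymphocytes. If the omission is deliberate, give the reason instead.

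State that the new line is for reporting only. Protocol 10.1.1 refers to the 15.1 limits as alert ranges, and 15.1 itself attaches no action to them.

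In the table, give low and high lymphocytes separate rows. Show newly occurring low values apart from those already low at baseline, as SAP 2.7.4.1 already does for newly occurring notable vital signs. Reconcile the note in SAP Table 2-4 with the list by saying which tests can be flagged in both directions.

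The cost is one criterion and one table row, on data already collected. The downside is a few more flagged values, some present at baseline after prior immunosuppressants; the baseline split handles those.

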#### Clinically notable vital signs

Notable values for Vital signs are defined in [Table 8-4](#).

No specific action is pre-defined within this protocol to respond to specific abnormal vital signs, as it will be decided by the investigator whether and which specific action needs to be taken to respond to any abnormal values, taking into account the overall status of the subject.

### 15.3 Appendix 2: Determination of Tuberculosis status

Determination of tuberculosis (TB) status will be required before administration of study treatment and should be performed as defined by local guidelines. TB status must be determined by medical history, signs, symptoms and TB central lab testing. Any significant findings will be recorded in the relevant TB assessment eCRF and the Medical History eCRF, as necessary.

A central lab testing will be performed to assess the TB status at screening for all subjects. This test will only be used to determine subject's eligibility for the trial. The test will be used to screen the subject population for latent tuberculosis infection ([Doherty et al 2008](#)).

This blood-based assay is specific for *Mycobacterium tuberculosis* and is not influenced by previous *Bacillus Calmette-Guérin* vaccination or by exposure to other *Mycobacteria* species. Furthermore, this test, in contrast to the purified protein derivative (PPD) skin test, is also insensitive to a booster effect since the subject is not exposed to the vaccine. The assay measures the production of interferon-gamma and presents it relative to a negative and a positive control sample ([Manuel and Kumar 2008](#)). The tuberculosis assay test will be supplied by the central laboratory. Details on the collection, shipment of samples and reporting of results by the central laboratory are provided to investigators in the study-specific laboratory manual.

Positive or indeterminate tests must be recorded on the Tuberculosis assessment eCRF; the workflow of sample handling in case of positive or indeterminate test results is provided in [Figure 15-1](#).

- a. If the test result is **negative**, the subject may be randomized.
- b. If the test result is **positive**, the investigator should perform a work-up for the test result as per local procedures. If a TB work-up was conducted prior to the screening of the subject, results of the work-up can be used to assess eligibility if the work-up was conducted within 12 weeks prior to randomization.

Subjects **positive** for latent TB per work-up may be randomized to the trial if sufficient treatment has been initiated according to local routine clinical practice and will be maintained for the prescribed duration. Subjects positive for active TB per work-up are not eligible for the study. Subjects negative for TB (no signs of latent or active TB) per work-up may be randomized to the trial.

[figure not shown]
- c. If the test result is **indeterminate**, the investigator **may repeat the test once or may proceed directly to perform the work-up** for the test result as per local procedures. This action is at the discretion of the investigator. If a TB work-up was conducted prior to the screening of the subject, results of the work-up can be used to assess eligibility if the work-up was conducted within 12 weeks prior to randomization.

- i. If the second test is, the subject may be randomized.
- ii. If the second test is positive or indeterminate, the investigator should perform workup as per local guidelines. Subject positive for **latent** TB per workup may be randomized to the trial if sufficient treatment has been initiated according to local routine clinical practice and will be maintained for the prescribed duration. The subject will not be eligible for randomization if “active tuberculosis is present ”or“ latent tuberculosis is present” and is untreated per local guidelines.

iii. Subjects negative for TB per workup (no signs of latent or active TB) may be randomized to the trial if the workup was conducted 12 within weeks prior to randomization. .

If eligibility is being assessed with only 1 test result and a TB work-up (i.e., no second TB test will be performed), the TB test to assess eligibility must have been done via the central laboratory for the study within the Screening Period (within 4 weeks prior to randomization) and TB work-up will only be considered if it was completed **within 12 weeks** prior to randomization.

Figure 15-1 Tuberculosis screening flowchart

The subject will not be eligible for randomization if "active tuberculosis is present" or if "latent tuberculosis is present and is untreated as per local guidelines."

\* If the first QuantiFERON® TB-Gold In-Tube test (QFT) is indeterminate, the investigator may choose to perform a second QFT or refer the subject for tuberculosis workup per local guidelines.

\*\* If the result of any QFT is "positive" or the results of 2 sequential QFTs are "indeterminate", the subject must be referred to have a tuberculosis workup per local guidelines (if no workup within 12 weeks prior to randomization is available).

**Document History – Changes compared to previous final version of SAP**

Date	Reason for update	Outcome for update	for	Section and title impacted (Current)
2020/7/17	Creation of final version	N/A - First version	NA	
2021/11/23	To address comments during dry run preparation	• Amendment 1		
• Section 2.4.1: clarified the definition of duration of exposure.
 
• Section 2.6: specified the use of data after treatment discontinuation for secondary endpoints.
 
• Section 2.7.1: added analyses of exposure-adjusted incidence rate of AEs and risks.
 
• Section 5.4: clarified the description of the estimand framework.
 
• Section 5.5.2: added the section “Multiple imputations for supplementary analysis: Hypothetical scenario”.
 
• Section 5.6: Rule of exclusion criteria of analysis sets. Added a PD “M-INCL05-randomized in error” which causes subjects to be excluded from the Randomized set.

2021/12/14	To clarify endpoints and analyses following dry run completion	• Amendment 2		
• Section 1.1 and 2.14: removed the descriptions no longer applicable after dry run.
 
• Section 2.3.2: updated the disease history variables that would be summarized in the baseline characteristics table.
 
• Section 2.6.1: added the analyses of Scalpdex by dimension.

---

2022/5/19 To add analysis for the final CSR • Amendment 3

- Table 2-1: updated the treatment group labels.
- Section 2.6.3: updated the BOCF imputation from treatment period 1 to the entire treatment period.

[REDACTED]

[REDACTED]

[REDACTED]

[REDACTED]

---

## List of abbreviations

AE	Adverse event
ALT	alanine aminotransferase
AST	aspartate aminotransferase
ATC	Anatomical Therapeutic Classification
CLP	Cutaneous lichen planus
CSR	Clinical Study report
DLQI	Dermatology Life Quality Index
FAS	Full Analysis Set
eCRF	Electronic Case Report Form
EOT	End of treatment
[REDACTED]	[REDACTED]
IGA	Investigator's Global Assessment
LP	Lichen planus
LPP	Lichen planopilaris
LPPAI	Lichen Planopilaris Activity Index
MedDRA	Medical Dictionary for Drug Regulatory Affairs
MLP	Mucosal lichen planus
NRS	Numeric Rating Scale
OLPSSM	Oral Lichen Planus Symptom Severity Measure
PBO	Placebo
[REDACTED]	[REDACTED]
[REDACTED]	[REDACTED]
PT	Preferred Term
[REDACTED]	[REDACTED]
PD	Pharmacodynamics
PRO	Patient-reported Outcomes
PSAD	Physician Assessment of Surface Area of Disease
Q2W	Once every 2 weeks

---

Q4W	Once every 4 weeks
RAP	Report and Analysis Process
RAS	Randomized Analysis Set
REU	Reticular Erythematous Ulcerative
SAE	Serious adverse event
SAP	Statistical Analysis Plan
SOC	System Organ Class

## 1 Introduction

Data will be analyzed by Novartis according to the data analysis [Section 12] of the study protocol that is available in [Appendix 16.1.1 of the CSR]. Important information is given in the following sections and details are provided, as applicable, in [Appendix 16.1.9 of the CSR].

This document covers statistical and analytical plans for the primary endpoint analysis i.e after all subjects have completed their Week 16 visit as well for the final analysis i.e after all subjects have completed the follow up period following the 32 week treatment period.

